## 9.6 Mucosal sampling

Mucosal secretion and biopsy samples will be collected at the timepoints indicated in [Appendix D](#). All participants in this trial will have consented to mucosal specimen collections. Participants assigned male sex at birth will provide semen, rectal secretions, and rectal biopsies. Participants assigned female sex at birth will provide cervicovaginal and rectal secretions, as well as cervical, vaginal and rectal biopsies. Small (~2-4 mm) tissue biopsies are obtained from the vagina and ectocervix using a speculum and from the rectum by anoscopy by experienced clinicians. The product administration and biopsy collection schedules per mucosal compartment and visit are described in detail in [Table 9-1](#), and also outlined in [Appendix D](#); however, fewer samples may be taken based on the judgment of the performing clinician. The number of biopsies collected per mucosal compartment and visit is shown in [Table 9-2](#). Following the first product administration, a participant may decline all or some of the mucosal biopsies or secretion collections, but they should be encouraged to continue with any collections that they deem acceptable until the end of the trial.

**Table 9-1 HVTN 128 Sampling and product administration schedule**

	D –14 W –2	D0 W0	D14 W2	D112 W16	D126 W18	D224 W32	D238 W34	D336 W48
Product Administration		X		X		X		
Blood collection	X	X	X	X*	X	X*	X	X
Rectal, cervicovaginal and seminal secretion collection	X		X	X*	X	X*	X	X
Cervical, rectal, and vaginal biopsy collection	X		X				X	X

\* Specimen collections to be done prior to the infusion

**Table 9-2 Biopsy and secretion specimen totals**

	D –14 W –2	D14 W2	D112 W16	D126 W18	D224 W32	D238 W34	D336 W48	Total
Rectal biopsies	2	2				2	2	8
Cervical biopsies	2	2				2	2	8
Vaginal biopsies	2	2				2	2	8
Semen	1	1	1	1	1	1	1	7
Cervical secretions	2	2	2	2	2	2	2	14
Rectal secretions	1	1	1	1	1	1	1	7

- At each biopsy visit, prior to biopsy, participants must be confirmed to be low-risk for HIV infection.

- Participants will regularly be tested for gonorrhea and chlamydia. Additionally, participants who were assigned female sex at birth will be tested for trichomoniasis and bacterial vaginosis at indicated visits and may be tested for hyphae/budding yeast (when clinically indicated) as outlined in [Appendix D](#). In addition to the predefined testing timepoints, such tests may be performed at any time according to the clinicians' discretion. Test results will be provided to participants and all participants who test positive for 1 or more of these infections will receive counseling, as well as treatment or referral for treatment as appropriate. Sample collection will not be performed or may be deferred to a later date within the visit window if a contraindication to sampling (eg, active STI) is present (as indicated below).
- If biopsy or secretion collections are delayed, they should be performed as soon as possible, within the visit window. Specimens should not be collected outside the visit windows specified in the HVTN 128 SSP. The participant should resume the collection schedule with the next collection unless there are circumstances that require further delay or permanent discontinuation of collections.

#### **Rectal secretions and/or biopsy sampling**

- For participants assigned female sex at birth and capable of becoming pregnant, a pregnancy test must be performed and be negative prior to any rectal mucosal sampling.
- Rectal sampling will not be performed (or may be deferred to a later date within the visit window) if there is a contraindication to rectal biopsy or secretion sampling, such as an active infection or inflammation of the colorectal area (such as an HSV-2 outbreak or inflamed hemorrhoids or colitis/diarrhea).

#### **Additional biopsy-specific criteria**

- Biopsies will be collected a minimum of 21 days from previous rectal biopsies.
- Participants must not have taken antithrombotic medications (except ASA and NSAIDs) for 5 days prior to the procedure. If a participant is taking these medications for medical reasons, biopsies should not be collected and these medications should not be interrupted.
- Participant should not currently be taking anticoagulants. For participants with recent anticoagulant use, a CRS clinician must consult with the HVTN 128 PSRT for approval prior to collecting any tissue biopsies.
- Participants should not have receptive anal sex and/or insert any foreign object or substance into the rectum for **5 days after** biopsy samples have been collected;

- Participants should contact the clinic if they experience an excessive amount of bleeding, have a temperature of more than 38.1°C (100.5°F), experience chills, or have pain that is not improving.

### **Cervicovaginal secretion and/or biopsy sampling**

- Participants who are age 21 or older must report having had a Pap smear within the 5 years prior to enrollment, with the latest result reported as normal, or ASCUS (atypical squamous cells of undetermined significance) with no evidence of high-risk HPV; if high-risk HPV testing was not conducted, the participant must report having had a Pap smear within the 3 years prior to enrollment, with the latest result reported as normal or ASCUS. Pap smear results must be verified by medical records.
- For a participant who is capable of becoming pregnant, a pregnancy test must be performed and confirmed negative prior to biopsy sampling. For cervicovaginal secretion sampling, a pregnancy test must be done on the same day but can be performed prior to or after sampling.
- Cervicovaginal mucosal secretions cannot be collected during menstruation but should be performed as soon as possible, within the visit window.
- Cervicovaginal biopsies may be collected within the visit window during menses at the clinician's discretion.
- Cervicovaginal secretions or biopsy sampling will not be performed (or may be deferred to a later date within the visit window) if a participant has an active genital tract infection or lesion at the scheduled timepoint.
- Additional biopsy-specific criteria:
  - Biopsies will be collected a minimum of 21 days from previous cervical and vaginal biopsies.
  - Participants must not have taken antithrombotic medications (except ASA and NSAIDs) for 5 days prior to the procedure. If a participant is taking these medications for medical reasons, biopsies should not be collected and these medications should not be interrupted.
  - Participant should not currently be taking anticoagulants. For participants with recent anticoagulant use, a CRS clinician must consult with the HVTN 128 PSRT for approval prior to collecting any tissue biopsies.
  - Participants should not have receptive vaginal sex and/or insert any foreign object or substance into the vagina for **7 days after** biopsy samples have been collected;
  - Participants should contact the clinic if they experience an excessive amount of bleeding, have a temperature of more than 38.1°C (100.5°F), experience chills, or have pain that is not improving.

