*Risks of Blood Drawing:* Blood drawing may cause pain and bruising and may infrequently cause a feeling of lightheadedness or fainting. Rarely, it may cause infection at the site where the blood is taken. Problems from use of an IV for blood drawing are generally mild and may include pain, bruising, minor swelling or bleeding at the IV site and rarely, infection, vein irritation (called phlebitis), or blood clot. Risk will be minimized by using sterile technique and universal precautions. Blood drawing may also cause anemia.

*Risks of IV Infusion:* The placement of an IV catheter can allow for the development of bacteremia because of the contact between the catheter and unsterile skin when it is inserted. This will be prevented through careful decontamination of local skin prior to catheter placement and through the use of infection control practices during infusion. Product contamination will be

prevented by the use of aseptic technique in the pharmacy and universal precautions during product administration.

*Risks of biopsy and secretion collections:* Collection of cervicovaginal secretions using menstrual cups or sponges can cause momentary discomfort during speculum or menstrual cup insertion and, in some cases, minor bleeding. Collection of rectal secretion samples using a rectal balloon sampling device can cause momentary discomfort during anoscope insertion and, in some cases, minor bleeding. Collection of semen can be embarrassing for the participant.

Possible complications of biopsies are bleeding and infection. These complications are rare and risks of these complications will be minimized by careful hemostasis by the clinicians and detailed education of the participants to report bleeding and/or fever after the procedures. As biopsies create breaches in mucosal integrity, the risk of HIV infection - if exposed - is potentially increased during wound healing. Therefore (and to allow for undisturbed wound healing) an abstinence period is required of the participants after each biopsy. Healing of the superficial wounds in mucous membranes caused by these shallow, small (~2-4mm) biopsies is rapid; by 5-14 days, healing is expected to be complete (in cervicovaginal tissue and within 3 days in rectal tissue) (54).

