In the proposed schedule, a minimum of 21 days between biopsy collections will be adhered to, and repetitious biopsies are not assumed to increase the risk as compared to a single biopsy. More than 300 biopsy collections have been performed at the Seattle HIV Vaccine Trials Unit in the past two years and thus far not a single complication has occurred. In MTN 007, 7 rectal biopsies have been collected three times within one month, respectively, in 65 volunteers. One participant (1.5%) reported grade 1 hematochezia, two participants (3.1%) reported grade 1 painful defecation, and three participants (4.6%) reported grade 1 anal pruritus (55). As the biopsies create superficial wounds in mucous membranes, healing is rapid. By 5-14 days, cervical healing is expected to be complete (54).

A review of 34 studies in which 8,330 cervical and vaginal biopsies were taken concluded that cervical and vaginal biopsies taken among special populations, including women living in high HIV prevalence areas, are also safe and well tolerated (56). As of May 15, 2018, HVTN 116 has conducted 472 rectal biopsy collections, 280 cervical biopsy collections and 339 vaginal biopsy collections in a total of 79 enrolled participants. One female could not undergo complete collections due to a vaginal reaction after the first biopsy collection; one reported embarrassment after vaginal collection, and one stinging from silver nitrate. Two participants reported rectal discomfort after anoscope insertion but tolerated the collections. There have not been any terminations to date due to discomfort with the procedures. Cervical and vaginal biopsies in one female participant were permanently discontinued due to recurring vaginitis of unclear etiology.

Regarding procedure-related events during HVTN 116, to date there has been one pre-syncopal event after the collection of vaginal/cervical/rectal biopsies that

resolved on its own; one report of minimal rectal bleeding discovered when wiping with toilet paper that resolved on its own; two reports of constipation (one treated with medication and another resolved on its own), and one report of rectal pain that resolved on its own.

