## Reproductive Status

19. **Volunteers who were assigned female sex at birth:** negative serum or urine beta human chorionic gonadotropin ( $\beta$ -HCG) pregnancy test performed prior to biopsy collection and/or study product administration.

20. **Reproductive status:** A volunteer who was assigned female sex at birth must:

- Agree to use effective contraception for sexual activity that could lead to pregnancy from at least 21 days prior to enrollment through the last required protocol clinic visit. Effective contraception is defined as using the following methods:
  - Condoms (male or female) with or without a spermicide,
  - Diaphragm or cervical cap with spermicide,
  - Intrauterine device (IUD),
  - Hormonal contraception, or
  - Any other contraceptive method approved by the HVTN 128 PSRT
  - Successful vasectomy in any partner assigned male sex at birth (considered successful if a volunteer reports that a male partner has [1] documentation of azoospermia by microscopy, or [2] a vasectomy more than 2 years ago with no resultant pregnancy despite sexual activity postvasectomy);
  - Tubal ligation
- Or be sexually abstinent until at least 4 months following the last study product administration.

21. **Volunteers who were assigned female sex at birth must also agree not to seek pregnancy through alternative methods**, such as artificial insemination or *in vitro* fertilization until after the last required protocol clinic visit

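### Vaginal abstinence after biopsy ends at day 7, up to 7 days before the protocol's own upper limit for healing; a condom instruction for days 8 to 14 would be a cheap improvement

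*Protocol*

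**What the plan says.** Protocol Section 4.8, in the paragraph on biopsy and secretion risks, says that biopsies breach the mucosa and that "the risk of HIV infection - if exposed - is potentially increased during wound healing". It gives this, together with undisturbed wound healing, as the reason for requiring abstinence after each biopsy. It then states the expected times: "by 5-14 days, healing is expected to be complete (in cervicovaginal tissue and within 3 days in rectal tissue". Later in the same section the range is repeated for the cervix alone: "By 5-14 days, cervical healing is expected to be complete".

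Section 9.6 sets the periods. After cervical or vaginal biopsy, participants should not have receptive vaginal sex or "insert any foreign object or substance into the vagina for 7 days after biopsy samples have been collected". After rectal biopsy, they should not have receptive anal sex or "insert any foreign object or substance into the rectum for 5 days after biopsy samples have been collected". No reason is given for either number. Inclusion criterion 24 in Section 7.1 refers only to a required period and gives no length.

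Several general safeguards exist:
- Section 9.6 adds that "Participants should contact the clinic if they experience an excessive amount of bleeding", and likewise for fever, chills or pain that does not improve.
- It also says "At each biopsy visit, prior to biopsy, participants must be confirmed to be low-risk for HIV infection".
- Appendix F schedules risk reduction counseling at every visit.
- Appendix G expects condoms with new partners of unknown HIV status, occasional partners, partners outside a primary relationship and partners known to have others.

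The SAP does not deal with this matter.

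**The concern.** The abstinence rule is there to cover wound healing. On the rectal side it outlasts the stated healing time. On the cervicovaginal side it ends inside the stated range, so a participant at the slow end could resume vaginal sex while a biopsy site is still open. That is the situation Section 4.8 sets out to avoid.

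The symptom instruction helps only if there are symptoms. Criterion 20 in Section 7.1 accepts an IUD or hormonal contraception, and the Appendix G condom expectation does not extend to a primary partner who is not known to have other partners. A participant in such a relationship who heals late and without symptoms can therefore follow every rule in the supplied text and have sex without a condom on day 8.

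What is at stake is a small, avoidable exposure for individual participants. No trial result depends on it.

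**Working it through.** The plan gives no calculation here to reproduce, so the check compares its stated durations.

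**Inputs**
- Abstinence (Section 9.6): cervicovaginal 7 days, rectal 5 days.
- Expected time to complete healing (Section 4.8): cervicovaginal 5 to 14 days, rectal within 3 days.
- Biopsy visits (Tables 9-1 and 9-2): D-14, D14, D238 and D336, which is four visits.
- Next scheduled visit or contact (Appendix F, nominal days): D0, D112, D336 and D350.

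**Margin = abstinence period minus healing time**
- Rectal: 5 − 3 = +2 days.
- Cervicovaginal, earliest stated healing: 7 − 5 = +2 days.
- Cervicovaginal, latest stated healing: 7 − 14 = −7 days.

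**Uncovered days per visit = max(0, healing day − 7)**
- Healed by day 7: 0 days.
- Healed on day 14: 14 − 7 = 7 days.
- Over four visits: 4 × 0 = 0 to 4 × 7 = 28 days. The 28 requires a participant who gives every biopsy and heals on day 14 each time.

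**When a clinic visit could pick this up**
- D-14 to D0: 14 days.
- D14 to D112: 98 days.
- D238 to D336: 98 days.
- D336 to D350: 14 days. D350 is a safety contact that may be made by email, text or telephone.

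On the nominal schedule, no scheduled clinic visit falls before day 14 after a biopsy. Visit windows are set in the SSP, which was not available, so actual intervals may differ. The biopsy visit itself is therefore the natural place to give any instruction for days 8 to 14.

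**What cannot be computed.** The documents give no distribution of healing times, so neither the proportion healing after day 7 nor an expected number of uncovered days can be derived.

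**The case against.** The strongest objections, and what stands of each:

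- **Seven days lies within 5 to 14.** Correct. A reader might infer that Sections 4.8 and 9.6 contradict each other, but they do not. The rule fits anyone healed by day 7 and stops short only for later healers.
- **The 14-day figure is soft.** This stands in part. Section 4.8 cites one study of cervical biopsies and does not say whether the range reflects variation between people, the timing of checks or a cautious bound. It is nevertheless the protocol's own figure, stated twice.
- **Exposure is low.** This stands. Appendix G requires no HIV-infected or drug-injecting partner in the last 12 months, low-risk status is confirmed before each biopsy, and Section 7.3.6 stops biopsies if risk rises. It limits the consequence without closing the gap, since the protocol requires abstinence of these same low-risk participants.
- **Experience with biopsies is reassuring.** Section 4.8 reports 280 cervical and 339 vaginal collections in HVTN 116 with few and minor events, and a review of 8,330 cervical and vaginal biopsies. This supports tolerability. As reported in the protocol, it gives no time to wound closure.
- **The instruction may exist elsewhere.** This stands as a limit. The consent form was removed from the review copy and the SSP was not supplied, so one cannot say that participants never receive such advice. The difference between Sections 4.8 and 9.6 is visible regardless.
- **Participants are contacted in between.** A reader might infer that nobody speaks to them before day 14. The documents do not support that. Section 9.5 and Appendix F footnote 3 require a contact to give results after HIV testing, testing takes place at D336, and D350 only confirms that results were given. That contact is not described as covering biopsy healing.

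**Conclusion.** The point holds as a cheap improvement to participant safety, at the level of something to consider. The cervicovaginal rule falls short of the protocol's upper healing limit by 7 days, while the rectal rule exceeds its limit by 2. The shortfall per visit is 0 to 7 days and matters only for participants who heal after day 7 without symptoms. The 28-day total is a worst case; a reader might take it as a typical exposure, but the documents give no frequency that would support this.

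The conclusion assumes that the 5 to 14 days in Section 4.8 describes real variation in healing, and it is limited to the supplied text. Absolute risk is low, and no endpoint, sample or analysis is affected.

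**What to change.** Keep the 7-day rule. Add one bullet after it in Section 9.6, for example: *From day 8 through day 14 after cervical or vaginal biopsy, participants should use a male (external) condom for any receptive vaginal sex.* Give it in the risk reduction counseling that Appendix F already schedules at each biopsy visit (D-14, D14, D238, D336). Check the consent form and SSP first. If they already say this, only Section 9.6 needs aligning; if not, all three should carry the same wording.

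The cost is one bullet and matching participant information. The burden is condom use for vaginal sex on up to 7 days after each biopsy visit, at most 4 × 7 = 28 days per participant assigned female sex at birth. It falls also on those already healed and is new only for those not already using condoms. It adds no abstinence, visit, sample or analysis.

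The bullet answers the HIV-exposure reason in Section 4.8. It does not secure undisturbed healing after day 7 and does not cover other inserted objects.

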## **Semen sampling**

- Semen sampling will not be performed (or may be deferred to a later date within the visit window) if a participant is known to have an active genital tract infection at the scheduled timepoint.

## **9.7 HIV counseling and testing**

HIV counseling will be performed in compliance with the CDC's guidelines or other local guidelines for HIV counseling and referral. HIV testing will be performed in accordance with the current HVTN HIV testing algorithm following enrollment.

Participants will be counseled routinely during the trial on the avoidance of HIV infection.

Potential participants identified as being HIV-infected during screening are not enrolled. Potential and enrolled participants identified as HIV-infected will be referred for medical treatment, counseling, and management of the HIV infection. With respect to enrolled participants who become HIV-infected, see Section [9.14](#).

It is theoretically possible that an anti-HIV mAb may suppress viral replication, which can reduce the ability to detect HIV, even if a person is actually infected.

An anti-HIV mAb is not likely to directly reduce or inhibit the assays used to detect HIV-1 infection.

### **9.7.1 Study product-related seroreactivity**

Tests of human plasma containing VRC07-523LS have been conducted using a variety of commercially available HIV test kits. At high plasma concentrations, reactive or indeterminate results have been observed on some test kits. See the HVTN 128 SSP for further detail. Thus, there is a possibility that receipt of the study product will cause a reactive result on some currently available HIV test kits, especially if testing occurs close to study product administration timepoints.

Study staff will advise study participants to confine their HIV testing while in the study to that provided through the CRS. Staff will also inform study participants of the likelihood of routine HIV testing being offered or performed outside the study CRS at emergency rooms, clinics, and medical offices, and will inform participants of their right to opt out of HIV testing outside the study site. CRS staff should inform study participants if local and/or state/regional policies and regulations permit medical providers to perform HIV testing without first informing patients. If this is the case, then CRS staff should advise study participants that they may decline testing preemptively. CRS staff should also inform participants if positive results must be reported to local public health authorities. CRS staff should provide participants with CRS contact information

and should encourage participants to ask medical providers to contact the CRS. The CRS can verify that the participant is in an HIV mAb clinical trial and should only be tested at the study CRS.

## **9.8 Contraception status**

Contraception status is assessed and documented at every scheduled clinic visit for a participant who was assigned female sex at birth and who is sexually active in a way that could cause that participant to become pregnant. Prior to enrollment and throughout the study, staff will ask participants to verbally confirm their use of adequate contraceptive methods. A participant who was assigned female sex at birth and is sexually active in a way that could cause that participant to become pregnant should be reminded at all scheduled clinic visits of the importance of using contraception and should be referred to specific counseling, information, and advice as needed. (Specific contraception requirements are listed in Section [7.1](#)). This reminder should be documented in the participant's study record.

